#### **2.3.7. Medication Storage and Accountability**

The study investigators or the study coordinator will document the amount of study drug/placebo dispensed and/or administered to participants, the amount returned by participants, and the amount received from and returned to the UPMC-IDS. The study drug/placebo accountability records will be maintained throughout the course of the clinical trial.

#### **2.3.8 Concomitant Medications**

Potential participants will be asked during phone screening if prescribed medication on the exclusion criteria list. Potential participants will be asked to provide a list of concomitant medications at screening Visit 1. All candidates using vasoactive medications, unable to withhold warfarin (or use bridging therapy) prior to muscle biopsy, or unable to withhold thienopyridine medications for 5 days prior to muscle biopsy will be excluded. Participants taking daily aspirin, non-steroidal anti-inflammatory medications, or direct oral anticoagulants will be asked to hold 3

days prior to biopsy. If unable to hold aspirin, PI/study clinician will hold pressure after biopsy to prevent further bleeding for an additional 3 minutes.

### **2.3.9 Rescue Medications**

Not applicable

### **2.3.10 Randomization and Blinding:**

We will use the high quality pseudo-random deviate generator in SAS® (SAS Institute, Inc., Cary, North Carolina) to randomize participants to NO or placebo in 1:1 ratio. Because of the moderately large sample size and the resulting opportunity for participant characteristic imbalance between the arms and the threat it would pose to internal validity, we will employ an adaptive randomization scheme to ensure balance by design rather than chance with respect to some key characteristics. Specifically, stratified by study site, we will use a variation of the minimization algorithm that can account for both continuous and categorical variables to ensure balance with respect to gender and walking speed with 80% biased coin probability; and simultaneously guard against heavy sample size imbalance. Such adaptive schemes have been shown to be valid alternatives in trials. Study personnel will call in all prescriptions to the independent research pharmacist at the institutional Investigational Drug Service (See Resources and Environment), who will package all drugs/placebos to be similar in physical appearance. We have successfully employed the same process in other recently completed trials. Therefore, all participants and study personnel (except the study statistician and the dedicated provider of clinical care related to study safety) involved in assessments will be blind to treatment assignment.

## **2.4 STATISTICAL ANALYSIS**

### **2.4.1 Sample Size Justification**

The principle focus of the proof of mechanism trial is the impact of nitrite on mitochondrial energetics. To detect a significant difference in mitochondrial state 3 respiration in permeabilized fibers (the primary outcome for Aim 1), the planned sample size is 35 per group (a total of 70 participants). Respiration data from a previous multi-site RTC that was co-led by [name], showed a baseline values of  $270.30 \pm 99.80$  pmol/min/mg (mean  $\pm$  standard deviation) for State 3 respiration and a pre- to post-intervention change of  $68.5 \pm 97.61$  pmol/min/mg We conservatively anticipate a dropout rate of approximately 14%. Using published methods implemented in commercial software (PASS 2012®, Number Cruncher Statistical Systems, Kaysville, Utah), with 70 patients and 60 anticipated completers, we will be able to detect statistical significance of a difference as small as 71.80 pmol/min/mg in pre- to post-nitrite change with 80% power in a 2-tailed test at the  $\alpha=0.05$  level. The criterion for a minimally clinically important difference (MCID) has not been authoritatively established for the measure, but the above detectable difference corresponds to a moderate to large effect size ( $d=0.74$ ) by Cohen's criterion. Therefore, the planned sample size affords an appropriate level of statistical sensitivity to address the aims in a mechanistic study with proximal biological outcomes such as ours.

For Aim 3, with the anticipated 30+30 completers, we will be able to detect statistical significance of correlations as small as 0.49 and 0.35, respectively, between changes in mitochondrial energetics and changes in physical activity/function and fatigability with 80% power in two-tailed tests at  $\alpha=0.05$  conducted without and with stratification by treatment group. As such, the planned sample size will afford sufficient statistical sensitivity to detect even moderate associations between mitochondria respiration and clinical endpoints.

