Study Aims:	
Aim 1: To show efficacy of 12-weeks of sodium nitrite treatment to improve mitochondrial energetics.
 
Aim 2: To show efficacy of 12-weeks of sodium nitrite treatment to improve skeletal muscle perfusion.
 
Aim 3: To explore the effects of nitrite-induced changes in mitochondrial energetics on CRF and metrics of clinical function.
 
Overall, this protocol lays a mechanistically-oriented foundation for future studies to definitively assess the utility of nitrite treatment as an important therapeutic option for the growing burden of sedentariness in old age

Study Design:	Prospective, randomized, placebo-controlled, double-blinded trial at 2 clinical sites to study the utility of a 12-week intervention (oral nitrite capsules vs. placebo) in older (age $\geq 70$ years) healthy, sedentary adults (<1 hour of structured PA per week).
Planned Sample Size:	70 participants total
Duration of Treatment:	14 weeks (12 weeks of Intervention with 2 weeks of Post-intervention testing)
Major Inclusion Criteria:	
 
• Age <math>\geq 70</math> years
 
• Sedentary (<1 hour/week of volitional exercise activity)
 
• Clinically stable (euvolemic; baseline HR <math><100</math> bpm) and without hospitalization or invasive cardiac procedure for 6 weeks
 

Major Exclusion Criteria:	See complete list in section 3.3

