We will employ the same analytic strategy described above for the primary outcome mitochondrial respiration for each of our remaining secondary continuous outcomes of mitochondrial bioenergetics, skeletal muscle perfusion and clinical measures collected only pre- and post-intervention. The magnitude and statistical significance of the nitrite vs placebo contrasts will serve as formal tests of the hypotheses H1b-c and H2a-b.

**Aim 2:** For physical function and activity measures additionally assessed midway, and hypothesis H3a, we will instead employ a linear mixed model to accommodate multiple post-randomization assessments and the resulting stochastic non-independence of observations. Specifically, we will fit a series of linear mixed models with change from baseline in each measure of physical function/activity as the dependent variable; intervention arm (nitrite/placebo), follow-up time (mid-course assessments and 12 weeks) and their interaction as fixed effects; baseline value of the dependent variable as a fixed-effect covariate; and a participant random effect to account for multiple observations from each participant. We will appropriately construct means contrasts to make comparisons between intervention arms at each of the follow-up time-points, and interpret their statistical significance as supporting hypothesis H3a.

**Aim 3 (hypothesis H3b) Analysis:** We will examine whether changes in mitochondrial energetics, muscle perfusion and physical function/activity/fatigability tend to move at least partially in unison. We will compute Pearson and Spearman rank correlations between pre- to post-treatment changes in the above measures over the treatment period. We will consider correlations both with and without stratification by treatment group. We will also consider adjusting for baseline values of the measures considered and obtain partial correlation coefficients to isolate the associations in changes above and beyond any cross-sectional associations at baseline and comparing the correlations between groups using the Fisher's z-transformation. Finally, we will explore multivariable linear regression models with change in measures of physical function/ac-

tivity as the dependent variable; treatment group, and baseline and changes in measures of mitochondrial energetics as independent variables, taking care not to exceed the number of independent variables that could be realistically afforded by the effective sample size.

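### The two detectable correlations for Aim 3 are attached to the wrong analyses: about 0.35 belongs to all 60 completers and about 0.49 to the 30 in one arm

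*Combined protocol and SAP*

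**What the plan says.** The Aim 3 power statement is in section 2.4.1 (Sample Size Justification). It starts from 30 completers per arm ("For Aim 3, with the anticipated 30+30 completers"), in line with the Aim 1 paragraph ("with 70 patients and 60 anticipated completers"). At 80% power and two-sided alpha 0.05 it states that "we will be able to detect statistical significance of correlations as small as 0.49 and 0.35, respectively", and that the tests are "conducted without and with stratification by treatment group". It concludes that "the planned sample size will afford sufficient statistical sensitivity to detect even moderate associations between mitochondria respiration and clinical endpoints".

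The matching analysis is in section 2.4.2, Aim 3 (hypothesis H3b): Pearson and Spearman correlations between pre- to post-treatment changes. That section says "We will consider correlations both with and without stratification by treatment group", and it also plans "comparing the correlations between groups using the Fisher's z-transformation". The synopsis presents Aim 3 as exploratory: "To explore the effects of nitrite-induced changes in mitochondrial energetics on CRF and metrics of clinical function". Neither section restates or corrects the two detectable values.

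**The concern.** The word *respectively* ties 0.49 to the unstratified analysis and 0.35 to the stratified one. For separate tests within each arm this cannot be right: at the same power and alpha, a test in 30 people cannot detect a smaller correlation than a test in 60.

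The consequence is for interpretation. A reader who relies on section 2.4.1 would expect 80% power at r = 0.35 within an arm. A null within-arm result could then be taken as evidence against an association that the trial had only about an even chance of detecting. The closing claim about moderate associations follows directly from these figures, so its scope depends on which figure belongs to which test.

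**Working it through.** **Inputs, all from section 2.4.1:** 30 completers per arm and 60 in total, power 0.80, two-sided alpha 0.05. Hence z(0.975) = 1.960 and z(0.80) = 0.842, with sum 2.802.

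**1. Detectable correlation (Fisher's z).** r = tanh[(1.960 + 0.842)/√(n − 3)]

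- n = 60: 2.802/√57 = 0.371, so r = 0.355
- n = 30: 2.802/√27 = 0.539, so r = 0.492

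A t-based critical value with bias correction gives 0.353 and 0.487. A bivariate-normal calculation gives 0.352 and 0.485. Both printed values are thus reproduced, but 0.35 at n = 60 and 0.49 at n = 30.

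**2. Power at the printed values.** Power = Φ[atanh(r)·√(n − 3) − 1.960], with atanh(0.35) = 0.365 and atanh(0.49) = 0.536.

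| Test | r | Fisher z | Bivariate normal | Pairing |
|---|---|---|---|---|
| n = 60 | 0.49 | 98.2% | 98.3% | as printed |
| n = 30 | 0.35 | 47.6% | 48.7% | as printed |
| n = 60 | 0.35 | 78.8% | 79.5% | swapped |
| n = 30 | 0.49 | 79.5% | 80.9% | swapped |

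Only the swapped pairing gives the stated 80%, to within about two percentage points.

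**3. Significance threshold.** Critical |r| = t/√(t² + n − 2). For n = 30, t = 2.048 and the threshold is 0.361; for n = 60 it is 0.254. An observed correlation of 0.35 in 30 people would not reach significance.

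**4. Number needed.** For 80% power at r = 0.35: (2.802/0.365)² + 3, which rounds up to 62 people (61 with the bias-corrected method). That is roughly the whole trial's completers, which again identifies 0.35 as the pooled figure.

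**5. Could other settings explain the printed order?** By Fisher's z:

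| Setting | Unstratified | Within one arm |
|---|---|---|
| One-sided 0.05 | 0.32 | 0.45 |
| 90% power | 0.40 | 0.55 |
| Two-sided alpha 0.025 | 0.39 | 0.53 |
| No dropout (70 and 35) | 0.33 | 0.46 |

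None gives 0.49 unstratified or 0.35 within an arm.

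**6. Other meaning of stratification.** Suppose the stratified analysis is a single test combined over the two arms.

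- Fisher z values combined with weights 27 + 27 = 54: r = tanh(2.802/√54) = 0.364, with power at r = 0.35 of Φ(0.365·√54 − 1.960) = 77%.
- Partial correlation adjusting for arm: r = tanh(2.802/√56) = 0.358.

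Both are close to the printed 0.35. The unstratified test of 60 is still 0.355, not 0.49.

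**The case against.** The strongest reply is that this is only an inverted phrase. Both numbers are correct for the planned completers, and section 2.4.2 lists the analyses in the order with, then without, under which 0.49 and 0.35 would be right. A statistical reader will probably spot it, and nothing in the design rests on it: the sample size is set by state 3 respiration, and Aim 3 is exploratory. That is fair and limits the consequences. It does not make the sentence right, because it is a formal power statement that the design does not deliver as labelled.

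Second, the plan does not define stratification, and the drop from 80% to 48% applies only to separate within-arm tests. That also stands. However, comparing the arms' correlations by Fisher's z needs one correlation per arm, which makes the within-arm reading the likelier one. On the combined reading, the unstratified 0.49 remains wrong.

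Third, quoting 0.49 for the pooled test promises less than the trial can do, so that half of the error is conservative. Agreed; the harm lies in the within-arm figure.

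Fourth, the documents set no threshold for a moderate correlation, so the closing sentence is not false in itself. Agreed; the point there is to state which analysis it covers.

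**Conclusion.** The concern holds. The two detectable correlations are transposed: about 0.35 (0.352 to 0.355 by method) for the unstratified test of 60, and about 0.49 (0.485 to 0.492) for a test within one arm of 30. If stratified means separate within-arm tests, the stated 80% power at r = 0.35 is really 48 to 49%. If it means one test combined over arms, the second figure is nearly right and the first is still wrong.

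This rests on 30 completers per arm as planned and on Pearson correlation with bivariate normal changes. Spearman would need slightly larger values without changing the order. The Aim 1 sample size and the primary test do not use these figures and are unaffected.

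**What to change.** In section 2.4.1, give the values as 0.35 and then 0.49 and keep the present order of analyses (unstratified first). Alternatively, keep the numbers and name the stratified analysis first, as section 2.4.2 does. State that stratified means a separate correlation in each arm, if that is the intention.

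Then limit the closing sentence: sensitivity to correlations near 0.35 applies to the pooled analysis, while separate within-arm tests reach 80% power only from about 0.49 upwards.

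The cost is a text correction in one paragraph. Sample size, endpoints, data collection and the H3b analyses in section 2.4.2 stay as they are. The stated sensitivity becomes less favourable within arms and more favourable for the pooled correlation.

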### **2.4.2 Data Analysis**

Overview: All statistical analyses will be performed and overseen by the study statistician [name] (see LOS) using SAS® version 9 (SAS Institute, Inc., Cary, North Carolina). Participant

flow will be summarized using a CONSORT diagram. Data will be summarized by intervention arm and time point as well as baseline to follow-up change using appropriate descriptive statistics. First, the baseline participant characteristics will be compared between the two arms. Any significant differences will be noted and accounted for as additional covariates in the sensitivity analyses. Second, main analyses to address the aims will be performed as outlined below using multiple imputation for missing data. The primary analysis will be performed to test the primary hypotheses H1a about the primary outcome of mitochondrial respiration (high resolution respirometry). Secondary analyses will be performed for remaining hypotheses, secondary outcomes and other exploratory analyses. Third, we describe below our primary approach to missing data and a set of sensitivity analyses by including additional covariates and ignoring missing data.

**Baseline Comparison:** Due to the adaptive randomization scheme, it is unlikely that baseline participant characteristics will be significantly different between the arms. If we do find any, they will be included as additional covariates in the sensitivity analyses. We will not alter the primary analytic strategy to preserve its a priori nature and predictability. We will use independent samples t- or Wilcoxon rank sum tests, as appropriate based on distributional properties, to compare continuous baseline characteristics between the intervention arms. For categorical baseline participant characteristics, we will use chi-square and Fisher's exact tests, as appropriate. Statistical significance of the intervention term will be interpreted as indicating the need to include them as covariates in sensitivity analyses.

**Aim 1 Analysis:** Analysis of covariance (ANCOVA) model using the SAS® GLM procedure with baseline to follow-up change in mitochondrial respiration (high resolution respirometry) as the dependent variable, intervention arm (nitrite/placebo) as the effect of main interest, and the baseline value of mitochondrial bioenergetics as a covariate. The magnitude and statistical significance at  $\alpha=0.05$  of the nitrite vs placebo contrast will serve as the formal test of the primary hypothesis H1a.

We will employ the same analytic strategy described above for the primary outcome mitochondrial respiration for each of our remaining secondary continuous outcomes of mitochondrial bioenergetics, skeletal muscle perfusion and clinical measures collected only pre- and post-intervention. The magnitude and statistical significance of the nitrite vs placebo contrasts will serve as formal tests of the hypotheses H1b-c and H2a-b.

**Aim 2:** For physical function and activity measures additionally assessed midway, and hypothesis H3a, we will instead employ a linear mixed model to accommodate multiple post-randomization assessments and the resulting stochastic non-independence of observations. Specifically, we will fit a series of linear mixed models with change from baseline in each measure of physical function/activity as the dependent variable; intervention arm (nitrite/placebo), follow-up time (mid-course assessments and 12 weeks) and their interaction as fixed effects; baseline value of the dependent variable as a fixed-effect covariate; and a participant random effect to account for multiple observations from each participant. We will appropriately construct means contrasts to make comparisons between intervention arms at each of the follow-up time-points, and interpret their statistical significance as supporting hypothesis H3a.

**Aim 3 (hypothesis H3b) Analysis:** We will examine whether changes in mitochondrial energetics, muscle perfusion and physical function/activity/fatigability tend to move at least partially in unison. We will compute Pearson and Spearman rank correlations between pre- to post-treatment changes in the above measures over the treatment period. We will consider correlations both with and without stratification by treatment group. We will also consider adjusting for baseline values of the measures considered and obtain partial correlation coefficients to isolate the associations in changes above and beyond any cross-sectional associations at baseline and comparing the correlations between groups using the Fisher's z-transformation. Finally, we will explore multivariable linear regression models with change in measures of physical function/ac-

tivity as the dependent variable; treatment group, and baseline and changes in measures of mitochondrial energetics as independent variables, taking care not to exceed the number of independent variables that could be realistically afforded by the effective sample size.

**Sensitivity Analyses:** We will perform a series of sensitivity analyses to ensure the robustness of our results against various assumptions. One such analysis will involve inclusion of gender and baseline participant characteristics significantly different between groups as additional covariates in the ANCOVA and linear mixed models above. Another will involve sensitivity of results to missing data handling techniques. In addition, if analyses of residuals from the models show violations of statistical assumptions, we will consider fitting models after Box-Cox transforming the continuous variables.

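### Apart from gender, the covariates in the adjusted sensitivity analyses are chosen by baseline significance tests between randomised arms, which makes them a weak check on prognostic imbalance

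*Combined protocol and SAP*

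**What the plan says.** The Overview of section 2.4.2 has the arms compared at baseline and then states: "Any significant differences will be noted and accounted for as additional covariates in the sensitivity analyses". The Baseline Comparison paragraph names the tests. For continuous variables it says "We will use independent samples t- or Wilcoxon rank sum tests, as appropriate based on distributional properties"; for categorical variables it uses chi-square or Fisher's exact tests. It ends with the selection rule: "Statistical significance of the intervention term will be interpreted as indicating the need to include them as covariates in sensitivity analyses".

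The Sensitivity Analyses paragraph carries the rule into the models and adds one fixed covariate: "inclusion of gender and baseline participant characteristics significantly different between groups as additional covariates in the ANCOVA and linear mixed models above".

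Three other statements limit the rule's reach:
- On the primary analysis, the Baseline Comparison paragraph says: "We will not alter the primary analytic strategy to preserve its a priori nature and predictability".
- The primary ANCOVA includes "the baseline value of mitochondrial bioenergetics as a covariate". The mixed models for H3a likewise include the baseline value of their own outcome.
- Section 2.3.10 stratifies allocation by site and uses minimisation "to ensure balance with respect to gender and walking speed with 80% biased coin probability".

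The plan does not say how many characteristics will be tested or at what significance level. Apart from gender, it lists no covariates for the sensitivity models. Neither site nor walking speed is named as a covariate in any model. The rule also speaks of an intervention term, which the listed two-sample tests do not contain.

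**The concern.** After randomisation, a baseline difference between arms arises by chance, so the test addresses a null hypothesis already known to be true. Its p-value measures the size of the imbalance relative to sampling error. It carries no information on whether the variable predicts change in respiration. Both are needed before an imbalance can distort the treatment estimate.

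Two errors follow. A variable unrelated to the outcome enters the model if it happens to differ. A strongly prognostic variable stays out if its imbalance is moderate, which with 35 per arm covers quite large differences. Gender apart, the covariate set is also unknown until the data are seen, although the same section values predictability for the primary analysis.

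What is at stake is how informative the covariate-adjusted robustness check is, for the primary outcome and for H3a. Agreement between the primary and adjusted results would reassure less than a reader would expect.

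**Working it through.** **Inputs from the plan (section 2.4.1).** 35 per arm randomised; 30 per arm expected to complete; SD of change 97.61 pmol/min/mg; detectable difference 71.80 pmol/min/mg; 80% power; two-sided 0.05.

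**Assumptions, not in the plan.** Each baseline test at 0.05; independent tests; 5 to 30 characteristics tested; partial correlation r of 0.3 to 0.5 between a covariate and the change score.

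**Step 1: the plan's own figure.** A two-sample t calculation (noncentral t) with 30 per arm and SD 97.61 gives a detectable difference of 71.80, or d = 71.80/97.61 = 0.736, at power 0.800. The figure reproduces and serves below as a yardstick.

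**Step 2: chance flags.** P(at least one) = 1 − 0.95^k; expected number = 0.05k.
- k = 5: 23%, expected 0.25
- k = 10: 40%, expected 0.5
- k = 20: 64%, expected 1.0
- k = 30: 79%, expected 1.5

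The expected number does not need independence. The probabilities do, and positive correlation between measures lowers them.

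**Step 3: what the test can see.** With 35 per arm the significance threshold is t(0.975, 68) × √(2/35) = 0.48 SD. An unminimised characteristic differs by at least 0.3 SD with probability 2 × [1 − Φ(0.3/√(2/35))] = 21%. Of those, about 0.05/0.21 = 24% would be flagged.

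**Step 4: what a missed imbalance does.** A covariate imbalanced by z standard errors, with partial correlation r with the change score, shifts the estimate by about r × z standard errors. At z = 1.64 (p = 0.10, not flagged):
- r = 0.3: 0.3 × 1.64 = 0.49 SE
- r = 0.5: 0.5 × 1.64 = 0.82 SE

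With SE = 97.61 × √(2/30) = 25.2 pmol/min/mg, these are about 12.4 and 20.7 pmol/min/mg, or 17% and 29% of 71.80. If adjustment for baseline respiration lowers the residual SD, the absolute shifts are smaller.

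**Step 5: simulation.** 20,000 trials, 35 per arm, simple randomisation, no treatment effect, ten independent covariates of which one has correlation 0.5 with the outcome. The baseline outcome is not modelled, so 0.5 is best read as a partial correlation.
- Some covariate was flagged in 40% of trials. In 87% of those, only non-prognostic covariates were flagged. The prognostic one was flagged in 5% of all trials.
- In 17% of trials the prognostic covariate differed by at least 0.3 SD without being significant. The false-positive rate there was 8.2% unadjusted, 8.2% under the test-based rule and 4.8% with the covariate prespecified.
- Mean SE of the treatment effect was 0.238 SD unadjusted, 0.242 SD under the rule and 0.208 SD prespecified.
- Over all trials the false-positive rate was 4.7% to 5.3% under all three approaches.

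**Step 6: walking speed.** Minimisation is meant to keep it balanced, so it should seldom reach significance and seldom enter a model. This is reasoning from the design; it was not simulated.

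**The case against.** The strongest reply is that the plan already covers most of the ground. Its main model is fixed in advance and adjusts for the baseline outcome, plausibly the most prognostic variable. Site, gender and walking speed are handled in the allocation. Gender is a fixed covariate in the sensitivity models. The test-based rule touches only a secondary analysis. All of this stands, and it limits the importance of the point.

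The figures are also open to challenge. The number of tests, their level, their independence and the size of r are all assumed. Many baseline measures here are plainly related (CPET, 400-metre walk, SPPB, activity), so the chance of at least one flag is probably below the independent-test figure. Since the primary model already includes baseline respiration, only the partial correlation counts, and it may be small for a covariate related to that baseline. These objections make the figures illustrative. They do not change the direction: a between-arm p-value still does not measure prognostic value.

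A reader might infer that the check does nothing about confounding, or that it adjusts only for the wrong variables. The documents do not support that. Gender always enters, and a prognostic variable imbalanced enough to be significant would be adjusted for. What the rule misses is moderate, non-significant imbalance in prognostic variables.

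**Conclusion.** The concern holds within limits. Apart from gender, the sensitivity covariates are selected by a criterion that ignores prognostic value, so the adjusted analyses are a weak check on prognostic imbalance. Under the stated assumptions, chance alone would flag at least one variable in 23% to 79% of trials (5 to 30 independent tests at 0.05). An unflagged covariate with partial correlation 0.3 to 0.5 and z = 1.64 would move the estimate by about 0.5 to 0.8 SE.

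It might be inferred that the primary result or its type I error is compromised. It is not: the plan explicitly shields the primary ANCOVA from the baseline tests, and the simulated overall false-positive rate stayed close to 5%. The sample size of 70 is unaffected. This is a minor point, worth acting on because the remedy is nearly free.

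**What to change.** In section 2.4.2, drop baseline significance tests as the rule for choosing covariates and report baseline characteristics by arm descriptively. Fix the sensitivity covariates before unblinded data are seen:
- the allocation factors: site, gender (already planned) and walking speed;
- a short list of baseline variables already collected, each justified by the investigators as prognostic for the outcome. Age, baseline peak VO2 and accelerometer activity are candidates; the documents do not themselves show that these predict change in respiration;
- in any model, omit a listed variable that is already there as the baseline value of the outcome.

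With all three candidates the model has six covariates plus arm and baseline outcome, eight terms for 60 expected completers, which is workable.

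The cost is a wording change, with no new data and slightly less analysis. The downside is that a chance imbalance in an unlisted variable would be displayed but not adjusted for.
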